is a 20-item scale measuring participants' positive and negative affect. Each item is a mood descriptor (e.g. interested). Participants are asked to rate their current mood using a 5-point scale (1 = very slightly or not at all; 5 = extremely). PANAS-SF consisted of two subscales: positive affect (PA) and negative affect (NA). Each subscale has 10-items. The PANAS-SF has been shown to have good internal consistency (Cronbach Alpha Coefficients: PA (past few weeks) = .87, NA (past few weeks) = .87).

Secondary Outcome measures (objective task performance)

Emotional Categorisation Task [ECAT], The ECAT assesses speed to respond to positive and negative self-referent personality descriptors. Sixty personality characteristics selected to be disagreeable (e.g. "domineering", "untidy", "hostile") or agreeable (e.g. "cheerful", "honest", "optimistic") are presented. Participants are asked whether they would like or dislike to be referred to as each characteristic. The task takes approximately 5 minutes to complete and assess the following dependent variables: % Accuracy of each condition (positive or negative words) and mean reaction time for correct responses for each condition (positive or negative words).

Emotion Recognition Memory Task [EMEM]. The EMEM measures recognition memory for affective words. Participants are presented with a series of words comprising the pleasant and unpleasant personality words that were previously presented to them in the ECAT, and a set of previously unseen distracter words. For each word, participants are required to report whether they have previously seen the word. The task takes approximately 10 minutes to complete and assesses the following dependent variables: % Accuracy of each condition (positive or negative words), misclassifications of each condition (positive or negative words), target sensitivity for each condition and response bias for each condition.

Activity/Assessment	T-1	T0	T1	T2	T3
	Pre-Study	Baseline	2 weeks post	Mid-	Post-
		(Week 0)	randomisation	Treatment (Week 5)	Treatment (Week 10)
Online Eligibility Screen (Appendix 3)	Х				
Informed Consent	Х				
Instruction call	Х				
Randomisation		X (post baseline assessment)			
Interventions: DCBT-I and Sleep Hygiene Education		X (6 dCBT-I sessions completed over a minimum of 6 weeks)			
Demographics		Χ			
Follow-up call			Х		
FERT (Appendix 8)		Х		Х	Х
Self-report Emotion Regulation: DERS, PSWQ, PTQ (Appendix 5c, 5d, 5g)		Х		Х	X
Mood instability		Х		Х	X

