The main efficacy analysis will be conducted on a modified intention-to-treat basis including all participants having at least one outcome. The primary analyses (emotional processing of faces) differences between treatment groups (dCBT-I and SHE), will be estimated with mixed linear regression models. The main objective of the statistical analyses is to assess the effect of dCBT-I on the primary outcome at the end of the intervention period, 10 weeks. To this end a linear mixed modelling will be employed. In such models, the continuous outcome variable measured at the post randomisation time points features as the dependent, the baseline value of the outcome, stratification factors (sex, age, depression severity and insomnia severity), treatment arm (dCBT-I or SHE), assessment time (5 or 10 weeks) and a treatment x time interaction term included as covariates. To account for correlation between repeated measures on the same individual a subject-varying random intercept will be included. Time will be considered as a categorical variable and model fitted assessed for inclusion of a random slope. Model assumptions will be checked using diagnostic plots. Modelling will be based on the assumption that data are missing at random and will be fitted using restricted maximum likelihood estimation. Results from all analyses will be summarised at 5 and 10 weeks with 2 sided 97.5 % CIs and we will present the data from both adjusted (including stratification variables) and unadjusted models. The adjusted model will be considered the primary analysis.

Handling missing data

The analysis will use statistical techniques for handling missing outcome data under a missing-at random assumption (MAR). The availability of the outcome data for the primary outcome at 10 weeks will be summarised by randomised group.

The mixed effects model implicitly accounts for data missing at random, however the data missingness mechanism will be explored. Logistic regression models will explore any association between baseline characteristics and availability of the primary outcome at 10 weeks. Missing primary outcome data will be reported overall and by randomised group. Covariates found to be predictive of missingness (P< 0.05) will be included in the analysis model in a sensitivity analysis of the primary outcome.

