compliers in the control group (CACE). For the primary CACE analysis, a sufficient level of adherence will be defined as completing at least 3 Sleepio sessions. The analysis will be performed using a two stage residual inclusion regression with randomisation as an IV. In the first stage, a regression of treatment receipt on randomisation will be conducted. In the second stage, a regression of the outcome on treatment receipt will be conducted, adjusting for the first-stage residual as covariates, as well as the same covariates as the intention-to-treat analysis. Bootstrapping will be used to obtain CI due to the two stage approach.

Exploratory analysis

Exploratory analyses will be conducted to assess the effect of dCBT-I on other expressions in the FERT (fear, anger, disgust, surprise, neutral), including the grouping of positive (happy, surprise) vs negative (fear, anger, disgust) expressions. We will also report and conduct exploratory analyses on reaction times and emotion misclassifications from the FERT. Emotion Misclassification is defined as the percentage of misclassifications for each emotion (Number of responses to each emotion when that emotion not displayed/Number of faces of all other expressions). Emotion reaction time is the calculated mean reaction time for correct responses for each emotion (if no correct responses, recorded as a missing value).

For the secondary objective tasks (ECAT, EMEM), we will further report and analyse % accuracy and % of misses (ECAT) and misclassifications of each condition (positive or negative words) and mean reaction time for correct responses for each condition (positive and negative words) (EMEM).

We will report sleep diary data collected as part of the dCBT-I treatment (in the intervention group) and also report % of participants scoring < 11 on the ISI and < 10 on the PHQ-9 after treatment, to provide a clinical context.

Possible predictors of treatment effects on the FERT will be analysed and reported. Specifically, we will investigate early/late chronotype, self-rated emotion regulation, high vs low depression scores (PHQ-9 dichotomised at 15) and worry as predictors of responses. Moderators will be assessed separately by repeating the primary analysis model and including an interaction term between randomised treatment and the moderator.

Sensitivity analysis

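### As written, the exploratory moderator model estimates moderation averaged over weeks 5 and 10 rather than at week 10, and it tests PHQ-9 as a two-group variable

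*Combined protocol and SAP*

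**What the plan says.** The moderator plan is in the SAP under Exploratory analysis: each moderator is taken one at a time, by refitting the primary model and "including an interaction term between randomised treatment and the moderator". The candidates are early/late chronotype, self-rated emotion regulation, worry and "high vs low depression scores (PHQ-9 dichotomised at 15". No cut-point is given for early/late, and neither emotion regulation nor worry is said to be split.

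The model being repeated is in the SAP under Primary outcome. Its outcomes are the post-randomisation measurements, with "assessment time (5 or 10 weeks) and a treatment x time interaction term included as covariates", baseline outcome and the stratification factors, and "a subject-varying random intercept will be included". Its stated purpose is to "assess the effect of dCBT-I on the primary outcome at the end of the intervention period, 10 weeks". The SAP lists week-5 FERT accuracy as a secondary outcome.

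For moderation, the SAP names no moderator-by-time term, no three-way term and no week-10 contrast. PHQ-9 at or below 15 versus 16 or above is a randomisation stratum, and depression severity is already a covariate in the primary model. The protocol's SPIRIT figure (Fig 2) describes the intervention as "6 dCBT-I sessions completed over a minimum of 6 weeks", and both documents label week 5 mid-treatment.

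**The concern.** The primary model lets the treatment effect differ by visit, but a single treatment-by-moderator term does not let the moderator effect differ by visit. The treatment-by-time term already in the model does not relax this, because it is the same for every moderator value. The coefficient is therefore a weighted average over a mid-treatment and a post-treatment visit. The SAP otherwise keeps these apart, with week 10 primary and week 5 secondary. If moderation grows as the programme is completed, the average understates it at the endpoint.

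The PHQ-9 split adds a second, independent loss, since everyone on the same side of the cut is treated as alike. Interaction tests in a trial sized for a 0.5 SD main effect have little precision to spare.

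**Working it through.** **Inputs from the SAP:** N = 200, 15% attrition, 1:1 allocation, effect size 0.5, two-sided alpha 0.05 (0.025 per co-primary outcome), PHQ-9 of at least 10 at entry, PHQ-9 strata of 15 or less versus 16 or more. **Assumptions (not in the documents):** the within-person correlation between visits (0.3 to 0.7), visit completion rates, and the baseline PHQ-9 distribution.

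**1. The plan's own figures.** n per arm = 2(1.960 + 1.282)² / 0.5² = 84.1, rounded up to 85. Then 170 / 0.85 = 200. Power with 85 per arm is 90.3% at alpha 0.05 and 84.6% at 0.025, so the stated 90% and 85% reproduce. The documents give no power or precision figure for moderation.

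**2. What the single term estimates.** Let moderation be d5 at week 5 and d10 at week 10. With a random intercept and complete data, the shared coefficient is (d5 + d10)/2.
- d5 = 0: 0.50 × d10
- d5 = d10/2: 0.75 × d10
- d5 = d10: 1.00 × d10

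The weight on week 10 drops if more data are missing there. With 90% and 85% completing weeks 5 and 10 it is 0.475-0.480. With 85% at both it is 0.498. With 95% and 80% it is 0.431-0.445. Adding treatment × moderator × time and moderator × time recovers d10 in full in every case tried.

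**3. Power.** Take 170 evaluable, a moderator split at its median and outcome SD 1. There are four cells of 42.5, so the standard error of the week-10 interaction is √(4/42.5) = 4/√170 = 0.307. The visit-averaged standard error is 0.307 × √((1 + ρ)/2), which is 0.247, 0.266 and 0.283 for ρ = 0.3, 0.5 and 0.7. For d10 = 1.0 SD at alpha 0.05:

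| True week-5 moderation | Week-10 contrast | Averaged term, ρ = 0.3 / 0.5 / 0.7 |
|---|---|---|
| 0 | 90% | 53% / 47% / 42% |
| 0.5 SD | 90% | 86% / 81% / 76% |
| 1.0 SD | 90% | 98% / 96% / 94% |

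For d10 = 0.5 SD the week-10 contrast has only 37% power. The averaged term has 42-53% even in its best case (equal moderation).

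**4. Information lost by the split.** The share kept is the squared correlation between the score and its two-group version. A normal score cut at its median keeps 2/π = 64% and loses 36%. For PHQ-9 on 10-27, cut at 15 or less versus 16 or more:
- Truncated-normal scores (underlying means 12-17, SDs 3.5-5.5) lose 31-40%, with about 21-68% in the high group.
- Over a wider set of shapes, including uniform and geometric, the loss is 28-36% whenever 25-67% are in the high group.
- With about 8-17% in the high group the loss is mostly 36-52%. At 2% it reaches 78%.

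A 30-40% loss makes 170 participants act like about 119 to 102 for that test (170 × 0.70 and 170 × 0.60).

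For chronotype there is no documented cut-point or distribution. If MSFsc were normal, a median split would lose 36% and a 20/80 split 51%, but nothing in the SAP says which applies.

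**The case against.** Four points on the other side have force.

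- **The SAP says an interaction term, not only one.** It may be shorthand, and the model it repeats is summarised at both 5 and 10 weeks. That makes the text ambiguous. It does not supply the missing terms, and a statistician following the sentence literally would fit the averaged model.
- **The target visit is not stated.** The moderator text names no visit, a week-5 FERT effect is itself hypothesised, and a visit-averaged predictor is a coherent exploratory target. This stands: averaging is not an error in itself, and it is the stronger test if moderation is constant.
- **Zero moderation at week 5 is an extreme case.** One might infer from the six-week minimum that no one can have finished treatment at the week-5 assessment, and so that the estimate is halved. The documents do not support that. The SAP's Measurements section keeps the week-5 assessment open for a further 5 weeks, the CACE analysis counts 3 sessions as sufficient adherence, and the mediation analysis expects change by week 5. The 50% figure is one end of a range.
- **The PHQ-9 cut is a randomisation stratum.** Testing treatment by stratum is conventional. That explains the choice but does not restore the information. A continuous term has its own cost, namely an assumption of linear moderation.

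**Conclusion.** The point holds as a cheap improvement to an exploratory analysis. As worded, the moderator model gives one effect averaged over weeks 5 and 10. The average recovers between half and all of the week-10 moderation when week-5 moderation lies between none and the same amount (complete data). Power is below the week-10 contrast in the first case and above it in the last. The PHQ-9 split costs roughly 30-40% of that moderator's information. This figure rests on assumed distributions with a reasonably balanced cut, and the loss is larger if few participants score 16 or above.

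Two stronger readings should not be drawn. The PHQ-9 figure cannot be carried over to chronotype, because the SAP gives no cut-point and early/late may simply name the dimension. Nor do the documents show that a real predictor would be missed because of this wording: with about 170 evaluable, moderation well below 1 SD between high and low groups may be missed under either model.

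**What to change.** Amend the SAP's Exploratory analysis section.

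1. For each moderator, include moderator, moderator × time, treatment × moderator and treatment × moderator × time. Report the week-10 contrast, with the visit-averaged estimate alongside.
2. Test moderation with continuous baseline PHQ-9 and continuous MSFsc. Keep the PHQ-9 stratum (15 or less versus 16 or more) as a covariate and for descriptive display. If an early/late display is wanted, state its cut-point in advance.
3. Check linearity of the moderation, and keep the exploratory label.

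This uses data already collected and changes only SAP wording and code. The costs are two more parameters per model, less power than the averaged term if moderation is equal at both visits (90% against 94-98% in the 1.0 SD example), and reliance on linear moderation.
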